6.6 Dose escalation and dose modification

Investigational or other study treatment dose adjustments and/or interruptions are not permitted.

6.7 Additional treatment guidance

6.7.1 Treatment compliance

Injections will be administered at site. This information must be captured in the source document, the appropriate CRF(s) and in the Drug Accountability log.

Pharmacokinetic parameters (measures of treatment exposure) will be determined in all participants treated with MIJ821, as detailed in Section 8.5.2.

6.7.2 Recommended treatment of adverse events

AEs must be treated according to local guidelines relevant for the symptoms.

Medication used to treat AEs must be recorded on the appropriate CRF.

6.7.3 Emergency breaking of assigned treatment code

Emergency code breaks must only be undertaken when it is required to in order to treat the participant safely.

Most often, discontinuation from study treatment and knowledge of the possible treatment assignments are sufficient to treat a study participant who presents with an emergency condition. Emergency treatment code breaks are performed using the IRT. When the investigator contacts the system to break a treatment code for a participant, he/she must provide the requested participant identifying information and confirm the necessity to break the treatment code for the participant. The investigator will then receive details of the

investigational drug treatment for the specified participant and a fax or email confirming this information. The system will automatically inform the Novartis monitor for the site and the study team that the code has been broken.

It is the investigator's responsibility to ensure that there is a dependable procedure in place to allow access to the IRT/code break cards at any time in case of emergency. The investigator will provide:

- protocol number
- participant number

In addition, oral and written information to the participant must be provided on how to contact his/her backup in cases of emergency, or when he/she is unavailable, to ensure that un-blinding can be performed at any time.

A participant cannot continue the study after an emergency break.

7 Informed consent procedures

Eligible participants may only be included in the study after providing (witnessed, where required by law or regulation), IRB/IEC-approved informed consent.

Informed consent must be obtained before conducting any study-specific procedures (e.g. all of the procedures described in the protocol). The process of obtaining informed consent must be documented in the participant source documents.

Novartis will provide to investigators in a separate document a proposed informed consent form that complies with the ICH E6 GCP guidelines and regulatory requirements and is considered appropriate for this study. Any changes to the proposed consent form suggested by the investigator must be agreed by Novartis before submission to the IRB/IEC.

Information about common side effects already known about the investigational treatment can be found in the IB. This information will be included in the participant informed consent and should be discussed with the participant during the study as needed. Any new information regarding the safety profile of the investigational drug that is identified between IB updates will be communicated as appropriate, for example, via an investigator notification or an aggregate safety finding. New information might require an update to the informed consent and then must be discussed with the participant.

The following informed consents are included in this study:

- Main study consent, which also includes:
 - A subsection that requires a separate signature for the 'Optional Consent for Additional Research' to allow future research on data/samples collected during this study
- As applicable, the Information Sheet for the Female Partner of Male Study Participants which highlights the need for the use of highly effective methods of contraception
- As applicable, Pregnancy Outcomes Reporting Consent for female participants or the female partners of any male participants who took study treatment

Women of child bearing potential must be informed that taking the study treatment may involve unknown risks to the fetus if pregnancy were to occur during the study and agree that in order to participate in the study they must adhere to the contraception requirements.

Male participants must be informed that if a female partner becomes pregnant while he is enrolled in the study, contact with the female partner will be attempted to request her consent to collect pregnancy outcome information.

A copy of the approved version of all consent forms must be provided to Novartis after IRB/IEC approval.

Participants will be asked to complete an optional Trial Feedback Questionnaire (TFQ) to provide feedback on their clinical trial experience.

As per Section 4.6, during a Public Health emergency as declared by Local or Regional authorities i.e. pandemic, epidemic or natural disaster, that may challenge the ability to obtain a standard written informed consent due to limits that prevent an on-site visit, Investigator may conduct the informed consent discussion remotely (e.g. telephone, videoconference) if allowable by a local Health Authority.

Guidance issued by local regulatory bodies on this aspect prevail and must be implemented and appropriately documented (e.g. the presence of an impartial witness, sign/dating separate ICFs by trial participant and person obtaining informed consent, etc.).

8 Visit schedule and assessments

The Assessment Schedule (Table 8-1) lists all study assessments and when they are performed. All data obtained from these assessments must be supported in the participant's source documentation.

Participants should attend on-site study visits as outlined in the assessment schedule (Table 8-1) or as close to the designated day/time as possible. This is especially important for the Day 2 visit at which primary efficacy assessments are performed. Missed or rescheduled visits should not lead to automatic discontinuation. In addition, the participant will be contacted by phone in between on-site visits (Follow-up call) to collect information about adverse events and concomitant medications. In case follow-up calls have to be shifted by +/- 3 days, follow-up calls can be replaced by on-site visits in accordance to the original visit schedule.

In case a visit is performed outside the schedule, subsequent visits shall be performed in accordance to the original visit schedule. In addition to the scheduled visits, participants may have unscheduled visits for safety monitoring purposes at the discretion of the Investigator. Data collected during unscheduled visits will be recorded in the unscheduled visit CRFs.

Participants who discontinue from the study or withdraw their consent/oppose the use of their data/biological samples should be scheduled for a final evaluation visit if they agree, as soon as possible, at which time all of the assessments listed for the final visit will be performed. At this final visit, the adverse events and concomitant medications not previously reported must be recorded on the CRF.

The "X" in the table denotes the assessments to be recorded in the clinical database or received electronically from a vendor. The "S" in the table denotes the assessments that are only in the participant's source documentation and do not need to be recorded in the clinical database.

Every effort will be made to draw the PK samples at the protocol specified timepoints. Other assessments (e.g., ECG, vital signs, etc.) will be taken prior to the PK sample.

As per Section 4.6, during a Public Health emergency as declared by Local or Regional authorities i.e. pandemic, epidemic or natural disaster that limits or prevents on-site study visits, alternative methods of providing continuing care may be implemented by Novartis as the situation dictates. If permitted/approved by local or Regional Health Authorities and Ethics Committees as appropriate and depending on operational capabilities, phone calls, virtual contacts (e.g. tele consult) or visits by site staff/ home nursing staff to the participant's home, can replace on-site study visits, for the duration of the disruption until it is safe for the participant to visit the site again.

Table 8-1 Assessment Schedule

Table 0-1	A336331	1101		JOHICO	iuic															
Period	Screening					Trea	tment						Follow-up							
Visit Name	Screening									Follow- up call	Follow- up visit	Follow- up call	Follow- up visit	Follow- up call		Follow- up call				
Visit Numbers ¹	1					20						40	50	60	70	80	90	100	110	120
Days	-28 to -1					1						2	4	8	11	15	18	22	25	29
Time (post-dose)	-	- 1h	0h	0.17h	0.33h	0.5h	0.75h	1h	1.5h	2h	4h	24h	•	-	-	-	-	-	-	-
Informed consent	Х																			
Inclusion / Exclusion criteria	Х	Х																		
Medical history/current medical conditions	×																			
SCID-5	S ³																			
MGH-ATRQ	S ³																			
Alcohol Test and Drug Screen	S ³	S ³																		
Pregnancy and assessments of fertility ⁴	Х	X ⁵																		х
Demography	Х																			
Body Height	Х																			
Body Weight	Х	Х																		Х
Physical Examination	S ³																			S ³

Period	Screening					Trea	tment									Follo	w-up			
Visit Name	Screening									Follow- up call	Follow- up visit	Follow- up call	Follow- up visit	Follow- up call	Follow- up visit	Follow- up call				
Visit Numbers ¹	1					20						40	50	60	70	80	90	100	110	120
Days	-28 to -1					1						2	4	8	11	15	18	22	25	29
Time (post-dose)	-	- 1h	0h	0.17h	0.33h	0.5h	0.75h	1h	1.5h	2h	4h	24h	-	-	-	-	-	-	-	-
Body Temperature	Х	X										Х								Х
Blood Pressure and Pulse Rate	Х	X ⁶				Х			Х		X	Х		X		Х		Х		Х
Respiratory rate ³	S	ഗ				S			S		S	S		S		S		S		S
Oxygen Saturation						S ^{3,7}	,													
Electrocardiogram (ECG)	Х	X ⁶				Х			Х		X	Х								Х
CADSS		Χ				Х			Х		Χ	Χ		Х		X		X		Х
MOAA/S		Χ				Х			Х		Χ	Χ		Х		Х		Х		X
Memory Assessment Questions ¹³						S					S	s								
C-SSRS	Χ	Х									Х	Х		Х		Х		Х		Χ
Local tolerability assessment						S					S	s								
Hematology	X ¹¹	Χ										Х								Χ
Clinical Chemistry	X ¹¹	Χ										Χ								Χ
Coagulation Panel	X ¹¹	X										Х								Х
Urinalysis	X ¹¹	Х										Χ								Х
PK blood collection ¹²			X8	Х	Х	Х	Х	х	Х	Х	X	X ⁹								

Pariod Carooning	Trootmo
Amended Clinical Trial Proto	ocol (Version No. 02, Clean)

Period	Screening					Trea	tment						Follow-up							
Visit Name	Screening									Follow- up call	Follow- up visit	Follow- up call	Follow- up visit	Follow- up call	Follow- up visit	Follow- up call				
Visit Numbers ¹	1		20 40							50	60	70	80	90	100	110	120			
Days	-28 to -1					1						2	4	8	11	15	18	22	25	29
Time (post-dose)	ı	- 1h	0h	0.17h	0.33h	0.5h	0.75h	1h	1.5h	2h	4h	24h	-	-	-	-	-	-	-	-
Randomization		Х																		
Dose administration			Х																	
MADRS	Х	Χ									Χ	Χ		Х		Х		Χ		Х
Concomitant therapies	Х	Х										Х	Х	Х	Х	Х	Х	Х	Х	Х
Adverse Events	Х	Χ	Х		Х		Х			Х	Χ	Χ	Х	Х	Х	Х	Х	Х	Х	Х
Study completion information																				Х
Safety follow-up call													Х		Х		Х		Х	

X Assessment to be recorded in the clinical database or received electronically from a vendor

1 Visit structure given for internal programming purpose only

2 Optional for participant

3 S = assessment to be recorded on source documentation only and will not be entered into the eCRF. If drug screen result is positive but does not meet DSM-5 criteria for substance use

- ⁴ Additional pregnancy testing may be performed at each visit to meet local requirements. Serum pregnancy test to be performed, unless specified otherwise.
- ⁵ Urine pregnancy test. Dosing can proceed only if result is negative.
- ⁶ Dosing can proceed if the results are deemed satisfactory by the Investigator.
- ⁷ Every 15 minutes from pre-dose to 4 hours post-dose
- ⁸ Pre-dose
- ⁹ Approximately 24 hours after the injection

disorder, the subject can be randomized.

- ¹¹ All screening laboratory results must be obtained before randomization to ensure participants eligibility
- ¹² In case of unscheduled visits for safety monitoring purposes during the time period from 4 hours to 24 hours after injection, unscheduled PK samples may be collected if operationally feasible.
- ¹³ The outcome of this assessment will only be captured in the eCRF if amnesia is considered as an AE

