9.1 Discontinuation from study treatment and from study

9.1.1 **Discontinuation from study treatment**

This is a single dose study, therefore treatment discontinuation for the individual participant is not applicable.

9.1.2 **Discontinuation from study**

Discontinuation from study is when the participant permanently stops further protocol-required assessments or follow-up.

If the participant agrees, a final evaluation at the time of the participant's study discontinuation should be made as detailed in the assessment table (refer to Section 8).

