- Drug interrupted/permanently discontinued
- 6. Its outcome: recovery status or whether it was fatal

Conditions that were already present at the time of informed consent should be recorded in medical history of the participant.

Adverse events (including lab abnormalities that constitute AEs) should be described using a diagnosis whenever possible, rather than individual underlying signs and symptoms.

Adverse event monitoring should be continued until EOS visit.

Once an adverse event is detected, it must be followed until its resolution or until it is judged to be permanent (e.g. continuing at the end of the study), and assessment must be made at each visit (or more frequently, if necessary) of any changes in severity, the suspected relationship to the interventions required to treat it, and the outcome.

Information about adverse drug reactions for the investigational drug can be found in the IB.

Abnormal laboratory values or test results constitute adverse events only if they fulfill at least one of the following criteria:

- they induce clinical signs or symptoms
- they are considered clinically significant
- they require therapy

Clinically significant abnormal laboratory values or test results must be identified through a review of values outside of normal ranges/clinically notable ranges, significant changes from baseline or the previous visit, or values which are considered to be non-typical in participant with the underlying disease. Alert ranges for laboratory and other test abnormalities are included in Appendix 1.

Dissociation and amnesia

Dissociation means a lack of connection within or between oneself and one's environment. It is not the same thing as "psychosis" which means fixed false beliefs (delusions) or false sensory experiences (hallucinations) but can be compared to the normal cognitive process of dreaming, where one is disconnected from one's body and the real world. Déjà vu and déjà entendu are classic dissociative experiences.

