#### **Treatment-emergent data**

The treatment-emergent data is defined as data collected after the study drug injection on Day 1. Considering the short follow-up duration (29 days after baseline) of this study, all safety data

after study treatment (except those collected after participant's withdrawal of consent) will be considered treatment-emergent. Similarly, the on-treatment period for the participants are defined as the whole study period from dose on Day 1 to EOS.

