## 2.4 Treatments (study treatment, rescue medication, concomitant therapies, compliance)

### 2.4.1 Study treatment / compliance

The study treatment is single injection of MIJ821 (10mg, 4mg or 1mg) or placebo on Day 1, the number of patients completed treatment will be reported by treatment arm based on SAF. Patients with protocol deviations related to treatment will be summarized in the PD summary table.

In case of unblinding during the study, any efficacy-related PRO data (including MADRS, [REDACTED]) collected after unblinding will be removed from the corresponding analysis. All safety data (including AE and safety-related PRO data) will be included in the corresponding analysis.

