## 2.6 Analysis supporting secondary objective(s)

### 2.6.1 Efficacy endpoint(s)

#### 2.6.1.1 Duration of antidepressant effect of MIJ821

##### Change from baseline in the MADRS total score over time

Derivation of the MADRS total score is covered in [Section 2.5.1.1](#). The change from baseline in MADRS total score will be summarized for all collected data (including 4-hour post-dose) by visit/timepoint and by treatment arms. In case of unblinding, the MADRS scores collected after patient's unblinding will be excluded in all the analysis. A listing of MADRS total score for each participant at each visit will be provided by treatment arm.

The change from baseline in MADRS total score at follow-up visits on Day 1 4 h post-dose, Day 2, 8, 15, 22 and 29 will be analyzed using the mixed-effects model for repeated measures (MMRM). This model will include the fixed, categorical effects of treatment, time (i.e. analysis visits), baseline MADRS score, class of anti-depressant standard of care, treatment-by-time and baseline MADRS score-by-time interactions. [REDACTED]

A summary table with model estimated means and their differences of each MIJ821 doses vs. placebo, will be obtained at each visit/timepoint, along with the 90% CI for the difference. Model estimated treatment means in change from baseline in MADRS score ( $\pm$ SE) will be plotted over time/visit for each arm.

[REDACTED TABLE]

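### An emergency code break ends study participation in a single-dose trial, so the scheduled safety assessments to Day 29 stop although no dosing remains to be stopped

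*Protocol*

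**What the plan says.** Protocol 6.7.3 restricts when the code may be broken: "Emergency code breaks must only be undertaken when it is required to in order to treat the participant safely". It adds that most emergencies can be managed without a break. It then closes, without exception: "A participant cannot continue the study after an emergency break".

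Protocol 9.1.1 says: "This is a single dose study, therefore treatment discontinuation for the individual participant is not applicable". Protocol 9.1.2 says: "Discontinuation from study is when the participant permanently stops further protocol-required assessments or follow-up".

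Three provisions limit what is lost:

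- Protocol 8 offers anyone who discontinues a final evaluation, if they agree and as soon as possible, with every assessment listed for the last visit. Adverse events and concomitant medications not yet reported are recorded then.
- Protocol 10.1.1 requires a detected adverse event to be followed until it resolves or is judged permanent. It also says: "Adverse event monitoring should be continued until EOS visit".
- Protocol 10.1.3 collects SAEs in randomized or treated participants to the end-of-study visit. After that, SAEs suspected to be related remain reportable.

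SAP 2.4.1 removes efficacy ratings made after unblinding but says of the rest: "All safety data (including AE and safety-related PRO data) will be included in the corresponding analysis". SAP 2.6.1.1 repeats the efficacy half: "In case of unblinding, the MADRS scores collected after patient's unblinding will be excluded in all the analysis". Under SAP 2.1.1.2, "the on-treatment period for the participants are defined as the whole study period from dose on Day 1 to EOS". SAP section 4 records no change from the protocol.

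**The concern.** Where dosing is repeated, withdrawal after a code break has a treatment consequence. Here the only dose has been given, so withdrawal removes information and nothing else.

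A code may be broken only when safe treatment requires it. The participants removed are therefore selected by a safety outcome, and their missing follow-up cannot be treated as unrelated to what it would have shown. Safety and tolerability are a secondary objective, the trial is meant to guide dose selection, and each arm has 14 participants. Protocol 4.1.3 relies on the C-SSRS at every visit because this population is at risk of suicide. SAP 2.7.1 plans a listing of adverse events that first appear or worsen after the Day 15 visit, to look for withdrawal or rebound. A participant removed on Day 1 or 2 has no scheduled contact in that period.

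The protocol is less restrictive elsewhere. The footnote to Table 6-2 keeps participants in post-dose follow-up even if they take prohibited medication, and section 8 says a missed visit should not automatically lead to discontinuation.

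**Working it through.** The plan states no figure on this point, so there is none to reproduce. The check is a count of scheduled contacts, a netting-off of what the final visit restores, and a scale for how often the rule might apply.

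**1. Contacts remaining after a break** (protocol section 3 and Table 8-1). On-site follow-up is on Days 2, 8, 15, 22 and 29; calls are on Days 4, 11, 18 and 25.

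| Time of break | On-site visits not held as scheduled | Calls not held |
|---|---|---|
| Day 1 | Days 2, 8, 15, 22, 29 (5 of 5) | 4 of 4 |
| Day 2, after the 24-hour assessment | Days 8, 15, 22, 29 (4 of 5) | 4 of 4 |

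A later break loses less.

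**2. Netting off one final visit, for a break on Day 2 after the 24-hour assessment.**

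- C-SSRS, CADSS, MOAA/S, blood pressure and pulse: 4 scheduled, 1 restored, 4 − 1 = 3 lost.
- ECG, haematology, chemistry, coagulation and urinalysis: 1 scheduled (Day 29), 1 restored, 1 − 1 = 0 lost in number, but taken soon after the break instead of at four weeks.
- All contacts: 4 visits + 4 calls = 8; 8 − 1 = 7 lost.

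If the participant does not agree to the final visit, nothing is restored.

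**3. Where the early visit falls in the analysis** (SAP Tables 2-1 to 2-3). Scales and vital signs taken on Days 3 to 11 are mapped to Day 8, leaving Days 15, 22 and 29 empty. ECG and laboratory results up to Day 4 are mapped to the 24-hour visit, leaving Day 29 empty. From Day 5 onward they are mapped to Day 29 although taken well before it.

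**4. The withdrawal/rebound period** (SAP 2.7.1). The cut-off is the actual Day 15 visit. The later contacts are the calls on Days 18 and 25 and the visits on Days 22 and 29. For a break on Day 1 or 2 all four are lost, and a prompt final visit falls before the period starts.

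**5. Size per participant.** 1/14 = 7.1% of an arm; 1/56 = 1.8% of the trial.

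**6. How often.** Neither document gives a code-break rate. Assume a rate p among the 3 × 14 = 42 participants on active drug. The expected number is 42p, and the chance of at least one is 1 − (1 − p)^42.

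| Assumed p | Expected number | Chance of at least one |
|---|---|---|
| 1% | 0.4 | 34% |
| 2% | 0.8 | 57% |
| 5% | 2.1 | 88% |

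**7. Protocol and SAP together.** After an emergency break, SAP 2.4.1 would still apply to final-visit data and to adverse-event and SAE follow-up. It would also apply after accidental disclosure of a medication number, which protocol 6.4.2 foresees and for which no rule ends participation. What 6.7.3 takes away is most of the scheduled data that SAP 2.4.1 would otherwise include.

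**The case against.** The strongest reply is that the two documents can be followed as written and that the loss is small. SAP 2.4.1 is a conditional rule for data that exist; it does not promise that visits continue. The final visit is a full safety battery, not only a check on the event that led to the break. Known adverse events are followed to resolution. Protocol 10.2.5 has events of special interest followed on site until they resolve or no safety risk remains, and SAEs stay reportable. Breaks should be rare.

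Most of this stands, and it rules out three stronger readings that a reader might infer:

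- *That all safety follow-up is lost.* It is not. The gap is the repeated assessments and calls between an early final visit and Day 29, chiefly late events that are new and not serious, and repeated suicidality ratings.
- *That the SAP contradicts the protocol or is void.* It is neither, as step 7 shows.
- *That the participants with the most serious events are removed, in proportion to dose.* Section 6.7.3 says a break is usually unnecessary, and section 10.2.5 makes discontinuation after severe symptoms optional, so many serious events would lead to no break. Protocol 4.2.1 and 4.5 report dose-related dissociation and sedation, so a dose-related loss is possible, but no code-break data show it.

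The reply does not explain why observation should stop when there is no treatment left to stop. The final visit depends on agreement and comes early. SAE collection runs to an end-of-study visit, and the protocol does not spell out how that applies to someone who has already left.

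**Conclusion.** The point holds within these limits. In a single-dose trial, 6.7.3 ends scheduled safety observation in participants selected by a safety event, with no exposure prevented. For a break on Day 1 or 2 the loss is 4 or 5 on-site visits and 4 calls, offset by at most one early final visit, and it includes every scheduled contact after Day 15.

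Probably few participants are affected, possibly none. The rates in step 6 are assumptions, and the 7.1% per participant is simple arithmetic on 14 per arm. Power and the primary analysis are not the issue: a 24-hour MADRS score obtained after a break would be excluded under the SAP anyway. The change is worth making because the information lost is linked to safety outcome, the arms are small, and the visits are already scheduled.

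**What to change.** Reconcile protocol 6.7.3 with protocol 9.1 and 10.1 and with SAP 2.4.1. State that an emergency code break does not by itself end scheduled safety data collection to Day 29, unless the participant declines or withdraws consent, and that MADRS scores after unblinding are excluded as the SAP provides. The statement should be confined to data collection; clinical care decisions stay as they are. The reference in 6.7.3 to discontinuing study treatment should be aligned with 9.1.1 in the same edit.

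The text is about one sentence and uses visits already in Table 8-1. It does need a protocol amendment, with the approvals listed in protocol 14.1. The other cost is that later safety ratings for that participant may be made by staff who know the treatment. SAP 2.4.1 already accepts safety data collected after unblinding, and a listing could flag them.
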